Variable	Conceptual definition	Operational definition	Measurement units	Type of Variable
Age	Years a person has lived since birth	Patient's age, recorded in the file.	Years	Quantitative
Sex	Difference in physical and sexual characteristics that distinguish men from women.	Classification of the patient as male or female	Male Female	Qualitative Nominal
Chronic comorbidities	Long-standing diseases directly related to obesity	Additional diseases recorded in the patient's record	None Diabetes mellitus Hypertension Cardiovascular GERD Dyslipidemia Hypothyroidism SAOS Depression Another	Qualitative Nominal
BMI	Universal unit for estimating the amount of body fat a person has.	BMI value recorded in the file, or calculated from weight and height, as: Weight (Kg)/ Size (m) ²	Kg/m ²	Continuous quantitative
Obesity level	Excess or a general excessive accumulation of fat in the body	Degree or level of obesity in the patient. Grade I: 30-34.9 Kg/m ² Grade II: 35-39.9 Kg/m ² Grade III: >=40 Kg/m ² Superobesity >50 Kg/m ² Super-super-obesity >60 Kg/m ²	I II III Superobesity Super-super-obesity	Qualitative ordinal
Duration of surgery	Time of the surgical process.	Time of surgery recorded in the file	Minutes	Quantitative
Trans-operative complications	Adverse events developed during surgery	Perioperative complications recorded in the record	None Bleeding Pneumothorax Organ injury Vascular injury Other	Qualitative Nominal
Postoperative complications	Adverse events developed after surgery	Postoperative complications recorded in the record or mentioned by the patient at follow-up	None GERD Bleeding Leakage Obstruction Diarrhea Embolism Other	Qualitative Nominal

STATISTICAL ANALYSIS

A database will be created in Excel, which will be downloaded into the statistical package SPSS v.26 in its MacOS version for data processing.

A descriptive analysis will be performed. For qualitative variables with frequencies and percentages. For quantitative variables, the descriptive analysis will consist of mean and standard deviation. In case quantitative variables have a non-parametric distribution, median and interquartile range will be used as descriptive statistics.

ETHICAL CONSIDERATIONS

The present research project was submitted to evaluation by the Local Health Research and Bioethics Committees for assessment and acceptance.

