Treatment used: _____

Psychological/Psychiatric Illnesses: No Yes

Enfermedad(es): _____

Time of evolution: _____ years

Treatment used: _____

Endocrine Diseases: No Yes

Enfermedad(es): _____

Time of evolution: _____ years

Treatment used: _____

GERD: No Yes

How was the diagnosis made?

Not performed Endoscopy SEGD Phmetry Other: _____

Treatment:

 IBP: _____
 Antacids: _____
 H2RA: _____
 Otro: _____

Previous abdominal surgeries: No Yes

Hernioplasty How many years ago?: _____

BariatricSleeve Y-Roux MGB Band Gastric balloon
Otra: _____

Caesarean section How many: How many years ago (last):

Other: _____

Nausea (that required medication) or vomiting in previous surgeries? No Yes No No Yes

Respiratory symptoms: Denied Rhinorrhea S Dyspnea Cough

Other: _____

Sleep apnea (STOP-BANG):

Do you have loud snoring (heard from another room): Yes No Yes No
Yes No No

Do you feel tired during the day: Yes No
Have you ever been told if you pause your breathing while sleeping: Yes No Yes

No Yes No No

Collar diameter >40 cm: Yes No

Current condition and physical examination

Current condition and physical examination

Current condition and physical examination

Current condition and time of evolution: _____

Previous nutritional treatment: No Yes Which one :

Previous medical treatment: no yes which one :

Neurológico

Conscientious: Yes No **Orientated:** Yes No **Cooperative:** Yes No

Musculoskeletal:

Mobility: Normal Limited None **Muscle tone:** Preserved Altered

Skin and adnexa

Hydration: Good Fair Poor

Coloration: Normal Pallor Icteric Other: _____

Head and neck

Symmetrical: Yes No **Palpable masses:** No Yes

Chest

Cardiac: Normal Murmur Arrhythmia Frémito Other: _____

Pulmonary: Normal Wheezing Rales Rales Other: _____

Abdomen

Pain: No Yes Superficial Deep **Location:** _____

Palpable masses: No Yes Location : _____

Previous incisions: No Yes Type/Location : _____

Megaliths: No Liver Spleen Other: _____

Hernias: No Umbilical Inguinal Other: _____

Extremities: Intact: No Yes Edema: No Yes

Capillary filling: Normal Abnormal

Pre-surgical

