I am able to work... *

1 2 3 4 5

Nothing at all

Very Much

The pleasure I get out of sex is... *

1 2 3 4 5

Nothing at all

Very Much

Reflux Scale

Please answer the following questions based on how you currently feel

How bad is your heartburn? *

Heartburn when lying down? *

Heartburn when standing up? *

Heartburn after meals? *

Does heartburn change your diet? *

Does heartburn wake you from sleep? *

Do you have difficulty swallowing? *

Do you have pain with swallowing? *

Do you have bloating or gassy feelings? *

Do you have bloating or gassy feelings? *

If you take medications, does this affect your daily life? *

How satisfied are you with your present condition? *

- Satisfied
- Neutral
- Dissatisfied

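### GERD is taken from the record alone before surgery but from the record or any patient mention after it, so unrecorded earlier reflux can be counted as postoperative GERD

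*Protocol*

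**What the plan says.** The table under Definition and operationalization of the study variables contains GERD twice.

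- **Before surgery** it is a category of chronic comorbidities, defined as "Additional diseases recorded in the patient's record".
- **After surgery** it is a category of postoperative complications. The concept is "Adverse events developed after surgery", but the operational rule is "Postoperative complications recorded in the record or mentioned by the patient at follow-up".

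The forms differ in the same direction.

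- **Appendix 1 (intake)** has one No/Yes item for GERD, then "How was the diagnosis made" with the options "Not performed Endoscopy SEGD Phmetry Other", then a treatment list. It has no symptom scale.
- **Appendix 2 (follow-up)** has a Reflux Scale headed "Please answer the following questions based on how you currently feel". Six of its items concern heartburn, from "How bad is your heartburn" to "Does heartburn wake you from sleep". Appendix 2 also has a Reflux row in which patients rate their condition against the time before surgery as aggravated, unchanged, improved or resolved.

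The only non-inclusion criterion is an incomplete record, so earlier GERD does not exclude a patient. The general objective concerns the incidence of postoperative GERD.

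**The concern.** The postoperative rule contains the baseline source and adds a second one. A patient with long-standing reflux that nobody wrote down is free of GERD at baseline, and becomes a GERD case on mentioning it at follow-up. The concept requires onset after surgery, but nothing in the operational rule checks it.

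Stratifying by recorded baseline GERD does not remove the problem, because these patients sit in the stratum without GERD.

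At stake is the meaning of the main result. A count that mixes old and new reflux is not an incidence. The baseline and postoperative GERD percentages, both of which the descriptive analysis will produce, are not measured in the same way.

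**Working it through.** The protocol gives no figure on this point to reproduce. Its minimum of 275 patients (Sample size) is used below only to turn percentages into patients.

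**Sources side by side**

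| | Before surgery | After surgery |
|---|---|---|
| Operational source | Record | Record or patient mention |
| Form | One No/Yes item, diagnostic method, treatment | Six heartburn items and a Reflux row |
| Symptom scale | None | Yes, no cut-off stated |
| Rule separating old from new | – | None |

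**Illustration.** None of these inputs is in the documents. Let R be the share with reflux both before and after surgery, unchanged; b the share of it that the baseline record captures; and f the share captured at follow-up. Assume the two captures are independent and that there is no true new GERD.

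With R = 25%, b = 60%, f = 90%:

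- Recorded before: R × b = 0.25 × 0.60 = 15.0%.
- Counted after: R × f = 0.25 × 0.90 = 22.5%.
- Old reflux that looks new, all patients: R × (1 − b) × f = 0.25 × 0.40 × 0.90 = 9.0%, or 0.09 × 275 ≈ 25 patients.
- The same among patients without recorded baseline GERD: 0.09 / (1 − 0.15) = 10.6%.

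**Range.** For R from 15% to 35%, b from 50% to 80% and f from 90% to 100%:

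- Low end (R = 15%, b = 80%, f = 90%): 0.15 × 0.20 × 0.90 = 2.7% of all patients; 0.027 / 0.88 = 3.1% of those without recorded baseline GERD.
- High end (R = 35%, b = 50%, f = 100%): 0.35 × 0.50 × 1.00 = 17.5% of all patients; 0.175 / 0.825 = 21.2% of those without recorded baseline GERD.

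**Second route, allowing true new disease.** Let u be the share with unrecorded earlier reflux, s the share of those who mention it at follow-up, and i the true new rate in the rest. The apparent rate is u × s + (1 − u) × i, so the excess over i is u × (s − i). With i = 10%, u from 2% to 20% and s from 30% to 90%, the excess runs from 0.02 × 0.20 = 0.4 points to 0.20 × 0.80 = 16 points. If u = 0 there is no bias.

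**What is built in.** Every point of the first range sets f above b, so the apparent rise from baseline is assumed. The false 'new' count is less dependent on that. With b = f = 60%, both percentages are 15.0%, yet 0.25 × 0.40 × 0.60 = 6.0% of patients still look new if capture is independent. If the same patients are captured both times, it is zero.

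**The case against.** Several counter-arguments have force.

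- **Baseline is not limited to tested disease.** The intake item is a direct question, and a 'Yes' with no diagnostic test is allowed. Preoperative endoscopy results are also collected. This stands. The contrast is one direct question against several symptom questions, not confirmed disease against hearsay.
- **No passage codes a heartburn answer as GERD.** This is also correct. The table speaks of complications the patient mentions, and the Reflux Scale is not linked to it. But no rule says what counts as a mention, so the possibility stays open.
- **The Reflux row looks back to before surgery.** It can flag earlier reflux that the record missed. It has no 'new' option, patients without medical conditions are told to skip it, and no rule links it to the GERD outcome. It helps with the repair but does not close the gap as written.

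A reader might infer three stronger things that the documents do not support:

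1. *That the study will show a false rise from before to after surgery.* No before/after comparison is specified; Statistical Analysis plans frequencies only.
2. *That the result is biased against hiataloplasty.* The hypotheses compare surgery with and without mandatory repair. One rule applied to both groups would tend to dilute a difference, rather than act against the repair in particular.
3. *That the false 'new' rate can be judged against the 20% in Sample size.* The protocol does not say what that percentage measures, and 10.6% refers only to patients without recorded baseline GERD.

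**Conclusion.** The mismatch between the two operational definitions is in the text and affects the main outcome. Following the plan as written *can* count unrecorded earlier reflux as postoperative GERD; that it *will*, or how often, cannot be said. The size depends on under-recording at intake and on how readily patients mention reflux later, and the documents quantify neither. The 9.0% of all patients (10.6% of those without recorded baseline GERD) is correct arithmetic on assumed inputs, with independent capture and no true new disease. It shows only that the effect need not be small. Because the definition is fixed in the protocol and can be repaired with data already on the forms, it should be changed before analysis.

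**What to change.** Amend the table of study variables as follows.

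1. Describe the record-or-mention count as the frequency of GERD or reflux at follow-up. Do not call it incidence or set it against the recorded baseline percentage.
2. For any new-onset or before/after figure, use the same source on both sides: GERD in the record before and after, among patients with GERD 'No' at intake. Beside it, report the record-or-mention figure with and without patients whose Appendix 2 Reflux row indicates reflux before surgery. State in advance which answers count, because 'aggravated' is ambiguous when there is no 'new' option.
3. Report the Reflux Scale as a separate postoperative symptom result with no baseline scale.

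Use of acid-suppressing medication should not serve as the common rule. Appendix 1 lists treatment under GERD already declared, whereas Appendix 2 asks in free text for all current medication without the indication. That would bring back a difference between the two sides.

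The cost is one revised definition and a recode of data already collected. The downside is that a record-only figure may miss new reflux in patients followed only by e-mail, which is why both figures are shown. It also reduces the misclassification without removing it, since recording can be incomplete at both times.

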The incidence of postoperative GERD in patients undergoing gastric sleeve surgery is a growing concern. The prevalence of GERD in the general population is considerable, and its occurrence or exacerbation after bariatric surgery represents a significant clinical problem. Moreover, the management of postoperative GERD involves additional costs for both the patient and the health care system, in terms of long-term medication, clinical follow-up and, in some cases, surgical reintervention. The complexity of this problem lies in the multifactorial nature of its etiology. Factors such as hypotonia of the lower esophageal sphincter and the presence of hiatal hernia contribute to the development of GERD. Therefore, it is imperative to explore surgical strategies that can mitigate this risk. One such strategy is mandatory hiataloplasty during sleeve gastrectomy, which, although not extensively investigated in this specific setting, has the potential to address one of the key etiologic factors of postoperative GERD.

However, the adoption of mandatory gastric sleeve hiataloplasty presents not only technical challenges, but also involves considerations of surgeon training, hospital resources, and acceptance of new surgical protocols. The need for a more preventive and comprehensive approach to bariatric surgery is clear, but requires a solid evidence base and adaptation of current surgical practices. This context raises a significant issue: should mandatory hiataloplasty be integrated into the gastric sleeve to reduce the incidence of postoperative GERD and improve long-term outcomes for patients undergoing bariatric surgery?

HYPOTHESIS

Alternative hypothesis

Mandatory hiatal hernia repair performed during gastric sleeve surgery significantly reduces the incidence of postoperative gastroesophageal reflux disease (GERD) compared to gastric sleeve performed without mandatory hiatal hernia repair.

Null hypothesis

Mandatory hiatal hernia repair performed during gastric sleeve surgery does not have a significant impact on reducing the incidence of postoperative gastroesophageal reflux disease (GERD) compared to gastric sleeve performed without mandatory hiatal hernia repair.

OBJECTIVES

General

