Electronic clinical records of patients over 18 years of age of indistinct gender who underwent gastric sleeve with hiataloplasty for obesity or overweight management in a hospital center specialized in bariatric surgery in Tijuana, Baja California.

Study period

March 2024 - July 2024.

Sample size

To calculate the sample size, the formula for prevalence studies for infinite populations was used, considering a confidence interval of 95% and a margin of error of 5%. The formula is presented below:

$$n = \frac{Z_{\alpha/2}^2 (p * q)}{d^2}$$

where,

$Z_{\alpha/2}$ = Z-score of a normal distribution $\alpha/2 = 1.96$

$p = 20\%$

$q = 100 - p = 70\%$.

d^2 = margin of error = 10

n= a minimum of 275 patients is required

Sampling

Non-probabilistic sampling will be used.

Inclusion and non-inclusion criteria

Inclusion criteria

- Patients over 18 years of age.
- Gender indistinct.
- Overweight, obesity grade I, II, III, super obesity or super-super obesity.

- Underwent gastric sleeve with hiataloplasty for obesity management at a high volume Tijuana hospital dedicated to bariatric surgery.

Non-inclusion criteria

- Patient records with incomplete information.

Description of the study

1. This study will be subject to review by the Research and Research Bioethics Committees of the hospital in question. Since this is a retrospective study, informed consent is not required.
2. After approval, the electronic clinical records of overweight and obese patients who meet the inclusion criteria and who underwent bariatric surgery for obesity management in Tijuana during the study period will be reviewed.
3. The following information of interest will be obtained from the file: age, sex, comorbidities, BMI, type of procedure, duration of surgery, final bleeding, immediate postoperative and transoperative complications. Patient follow-up information will also be obtained, which is obtained both in person for patients who can attend follow-up consultations and remotely by e-mail after sending a medical questionnaire and subsequent response from patients who reside in another city or country and therefore cannot attend their follow-up consultations in person.
4. Finally, the data will be captured in SPSS for statistical analysis.
5. To measure the quality of life of patients and the effectiveness of surgery, the Bariatric Analysis and Reporting Outcome System (BAROS) scale will be used.

Definition and operationalization of the study variables

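### The sample size rests on the width of a 95% confidence interval, but the stated analysis reports no interval and leaves a single-group GERD percentage open to an efficacy reading (minor)

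*Protocol*

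**What the plan says.** **Sample size.** The protocol states that "the formula for prevalence studies for infinite populations was used", "considering a confidence interval of 95% and a margin of error of 5" percent. The list under the formula gives p = 20%, q = 70%, and "d^2 = margin of error = 10". It concludes that "n= a minimum of 275 patients is required". No power, effect size or comparison group enters the calculation, and the outcome to which p = 20% refers is not named.

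**Statistical Analysis.** "A descriptive analysis will be performed". The next sentence sets the output: "For qualitative variables with frequencies and percentages". Quantitative variables get mean and standard deviation, or median and interquartile range. The abstract gives the same plan, without the median option. In the variable table, postoperative GERD is one category of a qualitative nominal variable (postoperative complications), so its planned output is a count and a percentage. The only confidence interval mentioned for the study's own data is the one in the sample-size paragraph.

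**Hypothesis and inclusion criteria.** The alternative hypothesis says "Mandatory hiatal hernia repair performed during gastric sleeve surgery significantly reduces the incidence of postoperative gastroesophageal reflux disease (GERD") relative to sleeve without mandatory repair. The inclusion criteria admit only patients who had sleeve with hiataloplasty.

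**The concern.** The one statistical property the sample size was chosen to deliver is the width of a 95% interval around a proportion. The analysis section lists the summaries to be produced, and that interval is not among them. Someone following the protocol would produce a point estimate without its uncertainty and would not report whether the intended precision was reached.

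This matters more here because the hypothesis and general objective are worded in terms of efficacy and significance, while the data come from one group. The most that group can supply is an incidence and its random error. A bare percentage that falls below some other figure, including the protocol's own planning value of 20%, could be presented as a reduction.

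**Working it through.** **1. The plan's own figure.** The formula is n = Z² × p × q / d², with Z = 1.96, so Z² = 3.8416. All inputs come from the Sample size section.

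| p | q | margin | n |
|---|---|---|---|
| 0.20 | 0.80 (that is, 1 − p) | d = 0.05 | 3.8416 × 0.16 / 0.0025 = 245.9, so 246 |
| 0.20 | 0.70 (as printed) | d = 0.05 | 3.8416 × 0.14 / 0.0025 = 215.1, so 216 |
| 0.30 | 0.70 | d = 0.05 | 3.8416 × 0.21 / 0.0025 = 322.7, so 323 |
| 0.20 | 0.80 | d = 0.10 | 3.8416 × 0.16 / 0.01 = 61.5, so 62 |
| 0.20 | 0.70 | d = 0.10 | 3.8416 × 0.14 / 0.01 = 53.8, so 54 |
| 20 | 80 | d² = 10, percent units | 3.8416 × 1600 / 10 = 614.7, so 615 |
| 20 | 70 | d² = 10, percent units | 3.8416 × 1400 / 10 = 537.8, so 538 |

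None of these gives 275. An unstated 10% allowance on the first row comes close (245.9 / 0.9 = 273.2, so 274), but the protocol mentions no allowance. The planned precision is therefore not settled. That is a separate defect, and it limits what can be said here about meeting a margin.

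**2. What 275 patients deliver.** The normal-approximation half-width is 1.96 × √(p(1 − p)/275).

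- p = 20%: 1.96 × √(0.16/275) = 4.7 points.
- p = 30%: 1.96 × √(0.21/275) = 5.4 points.
- The half-width equals 5 points when p(1 − p) = 275 × (0.05/1.96)² = 0.179, which is p of about 23.3%.

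Under the 5% margin, whether the target is met depends on the observed rate. Under a 10-point margin it is met in every case, because the half-width at p = 50% is 1.96 × √(0.25/275) = 5.9 points.

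**3. Intervals that would accompany the percentage.** The Wilson interval is centred at (x + Z²/2)/(n + Z²), with half-width Z√(p(1 − p)/n + Z²/(4n²)) / (1 + Z²/n). For 55/275:

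- Centre: (55 + 1.9208)/278.8416 = 0.2041.
- Half-width: 1.96 × √(0.0005818 + 0.0000127)/1.01397 = 0.0471.
- Interval: 15.7% to 25.1%.

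| Observed | Percentage | Wilson 95% interval |
|---|---|---|
| 41/275 | 14.9% | 11.2% to 19.6% |
| 55/275 | 20.0% | 15.7% to 25.1% (exact: 15.4% to 25.2%) |
| 82/275 | 29.8% | 24.7% to 35.5% |

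The counts are illustrations, not forecasts. The first row shows why an interval alone is not enough. It lies just below 20%, but 20% is a planning assumption and not a control rate, so even that result would be no evidence of a reduction caused by the repair.

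**The case against.** The strongest reply is that this is an omission and not a contradiction. The analysis section does not say that its list is exhaustive, both statements can be followed, and the choice of interval is commonly left to a statistical analysis plan, which may exist. Much of this stands. A reader might infer that the protocol rules out an interval, or that none will be reported; the text supports neither. What remains is that the protocol states its analysis twice, and neither statement includes the one quantity that justifies its sample size.

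Four further limits also stand.

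- A reader might take the sample size as explicitly built on GERD incidence. That is a reasonable inference from the title and objectives, but the protocol does not say it.
- A reader might conclude that the study misses its 5-point precision when the rate is near 30%. Because the margin is given as both 5% and 10, that cannot be asserted.
- A reader might say that the precision is hidden. It is not: a reported count with its denominator lets anyone compute the interval.
- A reader might expect an interval to rescue the hypothesis. It would not, because the hypothesis is comparative and there is one group. Sampling is also non-probabilistic and incomplete records are excluded, so a binomial interval describes random error only and not selection.

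Extending intervals to every complication rate would go beyond the mismatch, since the study was sized on a single proportion.

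**Conclusion.** The point holds as a minor one. The sample size rests only on the precision of a 95% interval for one proportion, the stated analysis does not report that interval, and the hypothesis invites a significance claim that one group cannot support. At 275 patients and a 20% rate the unreported uncertainty is just under 5 points either way (15.7% to 25.1%).

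This rests on three assumptions: that p = 20% refers to postoperative GERD, that 275 patients with known GERD status are available, and that observations are independent. It does not show that the stated margin will be missed, and adding the interval neither tests the comparative hypothesis nor corrects the sample-size inputs.

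**What to change.** 1. In the Statistical Analysis section, state that postoperative GERD incidence will be reported as count, denominator and percentage with a two-sided 95% confidence interval, naming the method (Wilson or exact).
2. In the same place, state that no significant reduction and no efficacy claim will be drawn from this single-group percentage, and that the interval reflects random error only, given the non-probabilistic sampling and the exclusion of incomplete records.
3. In the Sample size section, name the outcome to which p = 20% refers and reconcile the two margins (5% in the text, 10 in the list). Only then compare the achieved width with the planned margin.

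The cost is a few sentences in the protocol and one line of output. No further data are needed.
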